remaining medication group at the start of the third (month 13) window. Our primary comparisons are between “brochure-intervention” patients and “baseline” patients (matched in terms of eligibility) from the same provider. Each patient will only have one opportunity to receive a brochure, even if they subsequently meet eligibility criteria for receipt of a second, different brochure. This allows equal exposure to the intervention for all Veterans since the impact of a second brochure might be influenced by the first brochure.

Although our primary comparison is between patients of the same provider pre- and post-intervention, we will also collect data at non-equivalent control sites matched by geography who will not receive the intervention; all data on control patients will be from the Corporate Data Warehouse (CDW). Including additional control sites will allow us to address potential temporal trends in deprescribing over the timeframe of our study that are not due to our intervention. The use of separate control sites (rather than randomizing some PCPs at each intervention site to control conditions) was preferred due to concerns about potential contamination across intervention and control conditions within sites. For both the control sites and the pre-intervention baseline period, we will identify patients who would have been eligible for the study; patients meeting criteria for multiple cohorts will be randomly allocated to only one.

Study Cohorts

The intervention cohort will consist of eligible patients in one of the three medication groups with an upcoming PCP appointment during the study enrollment period. We will create a comparison historical control cohorts comprising eligible patients in each medication group who were seen by the same PCPs at the same sites as our intervention cohort eighteen months to one year before our intervention cohort window to allow for comparable follow-up time before the intervention commenced. Patients in the intervention cohorts will be excluded from the historical control cohorts.

Medication Groups

To be enrolled in the study intervention or control cohort, patients needed to meet eligibility criteria for one of three medication-based groups. We have selected three medication-based patient groups based upon variations in 1) type of potentially inappropriate use, 2) medication factors (potential benefit and harms of continued use), and 3) anticipated interest in deprescribing by patients and providers.

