Official Title: Engaging Patients to Promote Deprescribing

NCT Number: NCT04294901

Document Date: November 14, 2019

Statistical Power

Based on fiscal year (FY) 2017 data, we estimated that we would mail brochures to at least 1,990 PPI patients, 894 Diabetes-Hypoglycemia patients, and 758 Gabapentin patients during the study. For apriori statistical power analyses, we made the following assumptions based on our pilot data: an overall baseline deprescribing rate of 4.21%, a conservatively high intraclass correlation coefficient (ICC) of 0.05 (for non-independence among patients of the same provider), an average of 20 eligible patients per PCC or WHC provider, and a 20% attrition rate (i.e., patients who receive the intervention brochure but do not attend their clinic visit). With these assumptions, we determined that we would have 80% power (for two-tailed tests at $\alpha=0.05$) to detect deprescribing rates following the intervention as small as 6.55% overall for these low-end estimates of our projected sample. Moreover, even at these low-end estimates of the projected sample size, we determined we would have 80% power to detect an overall deprescribing rate as low as 15% among the combined intervention cohorts even if the ICC was as high as 0.1, the baseline deprescribing rate was as high as 10%, and/or the attrition rate was as high as 40%. Notably, a deprescribing rate of 15% was reasonable to expect given that we found similar or higher rates in our pilot study.

We conducted analyses using SAS.³

Endpoints & Covariates

The primary hypothesis was deprescribing would be greater for Veterans receiving the intervention brochure than for those in the historical control group.

The primary outcome was binary: deprescribing versus not, assessed via pharmacy dispensing data from the VA Corporate Data Warehouse (CDW). More specifically, six months from the index date, an analyst queried the CDW to determine medication outcomes (e.g., complete deprescribing, dose reduction). We selected 6 months because prescriptions are often filled as a 90-day supply and using a shorter observation window might not fully identify that the prescription was not refilled. We removed patients who died within six months from their index data from intervention and historical controls at the analysis stage to avoid misattributing deprescribing to the intervention rather than death.

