intervention effectiveness was moderated by the target medication. We did not expect a discontinuation rate of 100%, as patients may have an indication to remain on the medication. No adjustments were made to p-values or confidence intervals for multiple comparisons for the primary outcome.

No interim analyses were planned.

Missing Data

We examined the incidence of missing data by medication cohort (PPI vs. DM vs. Gaba). We expected very low rates of missing data, given that our primary analyses rely on CDW data. For missing data, we implemented a series of sensitivity analyses using imputation (coding as “missing” for categorical variables and imputed means for continuous variables) to assess the degree of bias that might be induced by missing data. The results did not change in direction or significance.

Methods for dealing with data transformations

We did not apply any data transformations. All data underwent standard preliminary visualization and quality screening to test for potential violations of assumptions (e.g., distributional assumptions regarding normality, homogeneity of variance, linear relationships, outliers, ceiling/floor effects).

Other analytical subsets

The intervention is designed to target and engage patients, but it is possible that the intervention may be more effective with certain providers. Therefore, a null hierarchical model was used to estimate intraclass correlations to characterize the percent variance explained at the patient, provider, and site levels.

We used HGLM to examine whether the likelihood of deprescribing changes over time at our control sites (instead of from the pre-intervention period) to rule out alternative explanations for the effect of our intervention that rely on temporal trends in deprescribing unrelated to our intervention (e.g., other deprescribing initiatives). We elected not to include temporal deprescribing trends in the manuscript since there was no evidence of significant temporal trends.

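### The control-site trend test is never set against the intervention-site change and is not stated to use the same cohort rules, so a non-significant result is weaker evidence against a temporal trend than the SAP implies

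*SAP*

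**What the plan says.** The primary comparison is before versus after within the same providers at the intervention sites (Protocol, Randomization and Statistical Analysis Plan; SAP, Interim & Final Analysis). The rules for filling each cohort are these:

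- **Intervention sites, later period.** Each primary care provider is randomised to a sequence of drug groups, with windows opening at months 1, 7 and 13. Patients enter from upcoming appointments, once only (Protocol, Randomization and Study Cohorts).
- **Intervention sites, earlier period.** Patients were seen by the same providers 18 to 12 months before the intervention window. Those eligible for several groups are allocated at random to one. In addition, "Patients in the intervention cohorts will be excluded from the historical control cohorts" (Protocol, Study Cohorts).
- **Control sites.** These are matched by geography, described as non-equivalent, and use warehouse data only. The rule is: "For both the control sites and the pre-intervention baseline period, we will identify patients who would have been eligible for the study", again with random allocation of multiply eligible patients (Protocol, Randomization).

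The SAP (Other analytical subsets) then fits a hierarchical model to change over time at the control sites, to "rule out alternative explanations for the effect of our intervention that rely on temporal trends in deprescribing unrelated to our intervention". It adds that the trends were left out of the manuscript because none was significant. It gives no control-site sample size, no interval, and no term comparing the two site types.

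**The concern.** The control sites are the only concurrent comparator in a before-after design. To show that the primary change is not a secular trend, the useful quantity is the difference between the change at intervention sites and the change at control sites. The SAP instead tests the control-site change alone against zero and treats non-significance as the answer. A non-significant test can reflect a small sample as easily as a flat trend.

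The two changes are also not like for like. At intervention sites the way a patient reaches a drug group differs between periods: provider window later, patient-level random allocation earlier. At control sites the same random allocation is described throughout. The earlier intervention-site cohort also loses anyone who appears later, and no control-site counterpart is stated. A shift that comes from assembling the cohorts could therefore sit in the primary estimate without appearing in the control-site series.

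**Working it through.** **1. The plan's own power figure.** Inputs from SAP, Statistical Power: "at least 1,990 PPI patients, 894 Diabetes-Hypoglycemia patients, and 758 Gabapentin patients"; baseline 4.21%; "a conservatively high intraclass correlation coefficient (ICC) of 0.05"; 20 patients per provider; 20% attrition; two-sided 5% test. Equal group sizes are assumed.

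- Mailed: 1,990 + 894 + 758 = 3,642. After attrition: 3,642 × 0.8 = 2,914.
- Design effect: 1 + 19 × 0.05 = 1.95. Effective size: 2,914 / 1.95 = 1,494 per period.
- Power for 4.21% versus 6.55% is 80.9%, against the stated 80%. The target difference is 6.55 − 4.21 = 2.34 points.

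The SAP's figure reproduces and is not in dispute. No such figure is given for the control sites.

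**2. What a non-significant control-site trend could hide.** Control-site size is not stated, so it is assumed here as a multiple of the effective 1,494, with the same rate. The half-width of a 95% CI around a flat trend is 1.96 × √(2 × 0.0421 × 0.9579 / n).

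| Assumed size | Power, trend of 2.34 points | Power, trend half as large (to 5.38%) | Half-width if flat |
|---|---|---|---|
| 0.25× | 29% | 11% | 2.9 points |
| 0.5× | 52% | 18% | 2.0 points |
| 1× | 81% | 32% | 1.4 points |
| 2× | 98% | 56% | 1.0 points |

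At 0.25×, a flat estimate would not exclude a trend as large as the target effect. At 1× or 2× it would, and the series would be informative. Without a size or an interval the reader cannot tell which case applies.

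**3. The one-sided exclusion.** Let f be the share of historical patients still on the drug who later enter the intervention cohort, and g the same share among those deprescribed. Neither is given in the documents. The historical rate after exclusion is

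0.0421(1 − g) / [0.0421(1 − g) + 0.9579(1 − f)].

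| f | g | Historical rate | Shift (points) |
|---|---|---|---|
| 0.1 | 0 | 4.66% | 0.45 |
| 0.2 | 0 | 5.21% | 1.00 |
| 0.3 | 0 | 5.91% | 1.70 |
| 0.3 | 0.1 | 5.35% | 1.14 |
| 0.3 | 0.3 | 4.21% | 0 |
| 0.5 | 0 | 8.08% | 3.87 |
| 0.5 | 0.2 | 6.57% | 2.36 |

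Whenever f exceeds g the historical rate rises, which shrinks the apparent brochure effect. Taking g as zero is the extreme case. Deprescribing includes dose reduction, and the PPI group accepts any dose (Protocol, Medication Groups), so some deprescribed patients stay eligible.

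**4. Drug mix.** The change of allocation mechanism between periods at intervention sites could alter the share of each drug group. The SAP's covariate list (Endpoints & Covariates) does not name the target drug, which enters as a moderator afterwards. The documents give no drug-specific rates, so neither size nor direction can be computed.

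**The case against.** The strongest reply is that the SAP claims little for this check. Its sentence covers only explanations that rely on temporal trends, and the protocol gives the control sites the same purpose. A reader might infer that the check was meant to rule out every non-brochure explanation, including artefacts of cohort assembly, and has failed. The documents do not support that, because they never make the claim. Provider emails at intervention sites (Protocol, Data collection procedures) are likewise a separate limit, which matching cohort rules would not remove.

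A reader might also infer from the exclusion arithmetic that a positive result could be an artefact. It could not arise from this source: if patients still on the drug are the likelier to re-enter, the rule raises the historical rate and masks an effect.

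Nor do the documents say that control sites follow a different rule on every point. Calendar windows and provider continuity are simply not stated for them. Eligibility, data source and random allocation are shared with the baseline period, and the appointment criterion may well carry over through eligibility.

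Finally, for secular trend alone, a control-site series without any exclusion is the cleaner one. Stripping its earlier period would put an artificial decline into it.

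All of this stands, and it narrows the point. It does not answer the missing contrast, the missing interval, or the absence of stated control-site counterparts to the drug windows and the exclusion.

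**Conclusion.** The concern holds in a limited form. The control-site test is separate from the primary comparison, has no stated precision, and uses cohorts that on the written rules are not assembled like the primary ones. Its non-significance is therefore weaker evidence against a temporal trend than the SAP implies. It is not worthless: with a control-site sample about as large as the intervention-site sample, a flat estimate would carry a half-width near 1.4 points against a 2.34-point target.

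The exclusion pushes the primary estimate toward no effect, by 1.7 points at f = 0.3 and g = 0, less as g rises, and not at all when f = g. Both shares are assumptions. The drug-mix difference could act in either direction and cannot be sized from the documents. The control-site figures rest on assumed sample sizes and on the SAP's baseline, ICC and attrition. This is a weakness in a supportive analysis that should be repaired; it does not show that the primary result is wrong.

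**What to change.** Keep the primary analysis as planned, and add the following to the SAP:

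1. Select control-site patients in both periods with the same calendar windows, appointment rule and one-entry rule as at the intervention sites. Give each control-site provider a randomly drawn dummy drug sequence with windows at months 1, 7 and 13.
2. Fit one hierarchical model to both site types. Report the period-by-site-type difference with its 95% CI beside the primary estimate, as a supportive analysis and whatever its significance.
3. Handle the cross-period exclusion in one of two ways: apply the same rule to both site types in that contrast only, or repeat the primary analysis and the contrast without it as a sensitivity analysis. In either case leave the stand-alone control-site trend unstripped, and report it with its interval.

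The cost is programming on warehouse data the protocol already collects, plus SAP wording. The statistical cost is precision. With SE² = [p₀(1 − p₀) + p₁(1 − p₁)] / 1,494 + 2p₀(1 − p₀) / n, where p₀ = 4.21%, p₁ = 6.55% and the control trend is flat, the half-width is about 2.6, 2.2 or 1.9 points at control-site sizes of 0.5×, 1× or 2×. The primary estimate has 1.6 points. Power for 6.55% is then 42%, 56% or 67%. This approximation is conservative, since it takes no credit for providers acting as their own controls. It is the reason the contrast should be supportive and not primary.

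### A non-significant control-site trend is left unreported, although it is the only check on calendar-time drift in a before/after primary comparison

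*SAP*

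**What the plan says.** Under Randomization, the protocol makes the same-provider before/after comparison primary and then adds a safeguard: "we will also collect data at non-equivalent control sites matched by geography who will not receive the intervention". The reason given is "Including additional control sites will allow us to address potential temporal trends in deprescribing over the timeframe of our study". Under Study Cohorts, the historical patients come from the same providers and sites as the intervention cohort, 18 to 12 months before its window. The protocol's Statistical Analysis Plan section confines the primary model to intervention-site providers, and the SAP (Interim & Final Analysis) does the same.

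The SAP (Other analytical subsets) fits a separate model to the control sites. Its purpose is "to rule out alternative explanations for the effect of our intervention that rely on temporal trends in deprescribing unrelated to our intervention". Its contrast is described only as being to "examine whether the likelihood of deprescribing changes over time at our control sites (instead of from the pre-intervention period", where the closing words are a parenthesis. The outcome is one sentence: "We elected not to include temporal deprescribing trends in the manuscript since there was no evidence of significant temporal trends".

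**The concern.** A change in deprescribing shared by all sites between the historical and intervention periods passes in full into the before/after difference. Patient and provider covariates do not remove it. The control-site analysis is the only part of the plan that addresses it, so its result bears directly on how the primary estimate is read.

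The SAP treats a non-significant test as settling the matter. A test that does not reject shows only that zero change is compatible with the data. The interval shows which other changes are compatible too, and the reader is not given it.

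It is also unclear what was tested. The protocol's "For both the control sites and the pre-intervention baseline period, we will identify patients who would have been eligible for the study" sets the control sites and the baseline period side by side without saying whether control-site data reach back to that baseline. The SAP's parenthesis can be read as saying that they do not. If they cover only the study windows, the test does not span the interval over which drift would bias the primary contrast.

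**Working it through.** **Inputs from the SAP (Statistical Power).** Brochures: 1,990 + 894 + 758 = 3,642. Attrition 20%, ICC 0.05, 20 patients per provider, baseline rate 4.21%, detectable rate 6.55%, two-sided α = 0.05.

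**Assumed, because the documents are silent.** A historical group equal in size to the intervention group; control sites k = 0.5, 1, 2 or 3 times that size per period; an upward drift of 0.5 or 1.17 points (1.17 is half of 6.55 − 4.21 = 2.34). These are unadjusted two-proportion calculations and do not reproduce the hierarchical model.

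**1. The SAP's own figure.** 3,642 × 0.8 = 2,914 per period. Design effect 1 + 19 × 0.05 = 1.95, so effective n = 2,914 / 1.95 = 1,494. SE = √[(0.0421 × 0.9579 + 0.0655 × 0.9345) / 1,494] = 0.82 points. Power = Φ(2.34/0.824 − 1.96) = 81%, against 80% stated. The inputs reproduce.

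**2. Two-period control-site test.** The 95% half-width around no change is 1.96 × √[2 × 0.0421 × 0.9579 / (k × 1,494)], which is 1.44 points at k = 1. For a drift to rate p₁, SE = √[(p₀q₀ + p₁q₁) / (k × 1,494)]. At k = 1 and 1.17 points, SE = 0.78, the test rejects 32% of the time and misses 68%.

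**3. False positive at the intervention sites.** With no brochure effect, the upper-tail rejection rate is Φ(drift/SE − 1.96): Φ(1.17/0.781 − 1.96) = 32%, and Φ(0.5/0.755 − 1.96) = 10%, against 2.5% with no drift. The two sets of sites are independent, so the joint probability is the product.

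| k | 95% half-width (points) | 0.5 points: missed | 0.5: missed and false positive | 1.17 points: missed | 1.17: missed and false positive |
|---|---|---|---|---|---|
| 0.5 | 2.0 | 92% | 9% | 82% | 26% |
| 1 | 1.4 | 90% | 9% | 68% | 22% |
| 2 | 1.0 | 85% | 8% | 44% | 14% |
| 3 | 0.8 | 79% | 8% | 26% | 8% |

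**4. Control data in the three study windows only.** With windows six months apart and k × 1,494 / 3 patients in each, the slope SE is √[p₀q₀ / (2 × k × 1,494 / 3)] = 0.64 points per window at k = 1. A drift of 1.17 points spread evenly over 18 months is 0.39 per window. It is missed 93%, 91%, 86% or 81% of the time for k = 0.5, 1, 2, 3 (64% to 94% if spread over 12 to 24 months). A 0.5-point drift is missed 90% to 95% of the time.

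**5. Without the clustering penalty** (n = 2,914, two periods, k = 1). A 0.5-point drift gives 85% missed, 15% false positive, 13% joint. A 1.17-point drift gives 45%, 55% and 25%.

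**6. Size against the effect.** 0.5/2.34 = 21% and 1.17/2.34 = 50% of the smallest detectable difference. Against a rise to 15% (15 − 4.21 = 10.79 points), the same drifts are 5% and 11%.

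**The case against.** A plan does not normally carry results, and the manuscript is not among the documents. The safeguard was planned, run and disclosed with its purpose and outcome, so nothing was dropped silently. Every magnitude above rests on assumed drifts and control-site sizes. A two-period check would detect a drift equal to the whole 2.34 points 52%, 81%, 98% or more than 99% of the time for k = 0.5, 1, 2, 3. The 1.95 penalty is probably too heavy for a within-provider comparison; without it, a 1.17-point drift is missed only 16% or 5% of the time at k = 2 or 3. Difference-in-differences also needs parallel trends at sites the protocol itself calls non-equivalent.

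Much of this is right, and it limits the claim. The drift figures are illustrations, and large control sites with data in both periods would make a good check. But this SAP is written in the past tense, reports the trend conclusion and records the choice not to publish it, so that choice is open to criticism. Whether the check was a good one depends on the control-site size and the periods, which are the items not given. Removing the penalty also raises the false-positive rate, and at k = 0.5 the joint error for 1.17 points becomes 38%. The parallel-trends difficulty is a reason to keep the added model secondary; it gives no reason to withhold the control-site estimate.

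**Conclusion.** The concern holds and should be fixed. Non-significance is not an adequate reason for omitting the one analysis meant to exclude calendar-time change, and the documents do not let a reader judge how strong that analysis was. This follows from the SAP's wording and needs no assumption.

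The consequence depends on the true effect. Near the detectable limit, a modest drift that the control-site test would often miss could account for a fifth to a half of the difference. At a rise to 15%, it would bias the estimate without explaining it. Those sizes rest on the assumed drifts and control-site numbers; neither document shows that any drift occurred, and no error in the primary estimate is claimed.

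**What to change.** Keep the before/after hierarchical model as primary, keep the SAP sentence as a record, and supplement it.

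1. Whatever the p-value, report beside the brochure estimate the control-site change in percentage points with its 95% interval, the calendar periods compared, and the control-site numbers per period.
2. State whether the control-site data cover the historical period. If they cannot, say that the check applies to the study period only.
3. If they do, or can be extracted (the protocol says "all data on control patients will be from the Corporate Data Warehouse (CDW"), add a sensitivity analysis labelled as added later: one all-site model with period, site type and their interaction, with provider random intercepts and period slopes as planned. Give the interaction with its 95% interval, also in percentage points, and state the parallel-trends assumption. Allow for site-by-period variation or, with only three intervention sites, show the change site by site. The SAP already looks at site-level variance ("a null hierarchical model was used to estimate intraclass correlations to characterize the percent variance explained at the patient, provider, and site levels"), but that null model does not address variation in the change over time.

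**Cost.** Items 1 and 2 need only fuller reporting of work already done. Item 3 needs one model and perhaps one data extraction, and it is less precise. Its SE is √[(p₀q₀ + pq)/n + 2p₀q₀/(kn)], with p = 6.55% and n = 1,494. Power at 6.55% falls from 81% to 42%, 56%, 67% or 71% for k = 0.5, 1, 2, 3. Assuming three control sites and a site-by-period SD s of 0.5 or 1.0 points (adding 2s²(1/3 + 1/3) to the variance), it falls further, to 37–57% or 27–35%. Ignoring that variation at k = 1 would raise the type I error from 5% to 9% or 19%. Without the clustering penalty or site variation, power would be 69%, 84%, 92% or 94%. Power at 15% stays above 99.9% under the SAP's main inputs without site variation. In the SAP's worst case (ICC 0.1, baseline 10%, attrition 40%) it falls from 84% to 44%, 59%, 70% or 74%. This loss is why item 3 belongs beside the primary analysis and should not replace it.
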